8. ETHICAL CONSIDERATIONS

8.1 COMPLIANCE WITH LAWS AND REGULATIONS

This study will be conducted in full conformance with the ICH E6 guideline for GCP and the principles of the Declaration of Helsinki, or the laws and regulations of the country in which the research is conducted, whichever affords the greater protection to the individual. The study will comply with the requirements of the ICH E2A guideline (Clinical Safety Data Management: Definitions and Standards for Expedited Reporting). Studies conducted in the US or under a US Investigational New Drug (IND) application will comply with US Food and Drug Administration (FDA) regulations and applicable local, state, and federal laws. Studies conducted in the European Union (EU) or European Economic Area will comply with the EU Clinical Trial Directive (2001/20/EC).

8.2 INFORMED CONSENT

The Sponsor's sample ICF (and ancillary sample ICFs such as a Child's Informed Assent Form or Mobile Nursing ICF, if applicable) will be provided to each site. If applicable, it will be provided in a certified translation of the local language. The Sponsor or its designee must review and approve any proposed deviations from the Sponsor's sample ICFs or any alternate consent forms proposed by the site (collectively, the "Consent Forms") before IRB/EC submission. The final IRB/EC-approved Consent Forms must be provided to the Sponsor for health authority submission purposes according to local requirements.

If applicable, the ICF will contain separate sections for any optional procedures. The Investigator or authorized designee will explain to each subject the objectives, methods, and potential risks associated with each optional procedure. Subjects will be told that they are free to refuse to participate and may withdraw their consent at any time for any reason. A separate, specific signature will be required to document a subject's agreement to participate in optional procedures. Subjects who decline to participate will not provide a separate signature.

The Consent Forms must be signed and dated by the subject or the subject's legally authorized representative before his or her participation in the study. The case history or clinical records for each subject shall document the informed consent process and that written informed consent was obtained prior to participation in the study.

The Consent Forms should be revised whenever there are changes to study procedures or when new information becomes available that may affect the willingness of the subject to participate. The final revised IRB/EC-approved Consent Forms must be provided to the Sponsor for health authority submission purposes.

Subjects must be re-consented to the most current version of the Consent Forms (or to a significant new information/findings addendum in accordance with applicable laws and IRB/EC policy) during their participation in the study. For any updated or revised

Consent Forms, the case history or clinical records for each subject shall document the informed consent process and that written informed consent was obtained using the updated/revised Consent Forms for continued participation in the study.

A copy of each signed Consent Form must be provided to the subject or the subject's legally authorized representative. All signed and dated Consent Forms must remain in each subject's study file or in the site file and must be available for verification by study monitors at any time.

8.3 INSTITUTIONAL REVIEW BOARD OR ETHICS COMMITTEE

This protocol, the ICFs, any information to be given to the subject, and relevant supporting information must be submitted to the IRB/EC by the Principal Investigator and reviewed and approved by the IRB/EC before the study is initiated. In addition, any subject recruitment materials must be approved by the IRB/EC.

The Principal Investigator is responsible for providing written summaries of the status of the study to the IRB/EC annually or more frequently in accordance with the requirements, policies, and procedures established by the IRB/EC. Investigators are also responsible for promptly informing the IRB/EC of any protocol amendments (see Section 9.6).

In addition to the requirements for reporting all AEs to the Sponsor, Investigators must comply with requirements for reporting SAEs to the local health authority and IRB/EC. Investigators may receive written IND safety reports or other safety-related communications from the Sponsor. Investigators are responsible for ensuring that such reports are reviewed and processed in accordance with health authority requirements and the policies and procedures established by their IRB/EC, and archived in the site's study file.

8.4 CONFIDENTIALITY

The Sponsor maintains confidentiality standards by coding each subject enrolled in the study through assignment of a unique subject identification number. This means that subject names are not included in data sets that are transmitted to any Sponsor location.

Subject medical information obtained by this study is confidential and may be disclosed to third parties only as permitted by the ICF (or separate authorization for use and disclosure of personal health information) signed by the subject, unless permitted or required by law.

Medical information may be given to a subject's personal physician or other appropriate medical personnel responsible for the subject's welfare, for treatment purposes.

Given the complexity and exploratory nature of exploratory biomarker analyses, data derived from these analyses will generally not be provided to study Investigators or subjects unless required by law. The aggregate results of any conducted research will

be available in accordance with the effective Roche policy on study data publication (see Section 9.5).

Data generated by this study must be available for inspection upon request by representatives of national and local health authorities, Sponsor monitors, representatives, and collaborators, and the IRB/EC for each study site, as appropriate.

8.5 FINANCIAL DISCLOSURE

Investigators will provide the Sponsor with sufficient, accurate financial information in accordance with local regulations to allow the Sponsor to submit complete and accurate financial certification or disclosure statements to the appropriate health authorities. Investigators are responsible for providing information on financial interests during the course of the study and for 1 year after completion of the study (see definition of end of study in Section 3.2).

9. STUDY DOCUMENTATION, MONITORING, AND ADMINISTRATION

9.1 STUDY DOCUMENTATION

The Investigator must maintain adequate and accurate records to enable the conduct of the study to be fully documented, including, but not limited to, the protocol, protocol amendments, ICFs, and documentation of IRB/EC and governmental approval. In addition, at the end of the study, the Investigator will receive the subject data, including an audit trail containing a complete record of all changes to data.

9.2 PROTOCOL DEVIATIONS

The Investigator should document and explain any protocol deviations. The Investigator should promptly report any deviations that might have an impact on subject safety and data integrity to the Sponsor and to the IRB/EC in accordance with established IRB/EC policies and procedures. The Sponsor will review all protocol deviations and assess whether any represent a serious breach of GCP guidelines and require reporting to health authorities. As per the Sponsor's SOPs, prospective requests to deviate from the protocol, including requests to waive protocol eligibility criteria, are not allowed.

9.3 SITE INSPECTIONS

Site visits will be conducted by the Sponsor or an authorized representative for inspection of study data, subjects' medical records, and eCRFs. The Investigator will permit national and local health authorities; Sponsor monitors, representatives, and collaborators; and the IRBs/ECs to inspect facilities and records relevant to this study.

9.4 ADMINISTRATIVE STRUCTURE

The Sponsor of the trial is F. Hoffmann-La Roche Ltd. The Sponsor has contracted PRA, who will be delegated responsibility for various aspects of this clinical trial.

One site will participate to enroll 16 subjects.

Central facilities will be used for certain study assessments throughout the study (e.g., specified laboratory tests and PK analyses), as specified in Section 4.5. Accredited local laboratories will be used for routine monitoring; local laboratory ranges will be collected.

9.5 PUBLICATION OF DATA AND PROTECTION OF TRADE SECRETS

Regardless of the outcome of a trial, the Sponsor is dedicated to openly providing information on the trial to healthcare professionals and to the public, both at scientific congresses and in peer-reviewed journals. The Sponsor will comply with all requirements for publication of study results. For more information, refer to the Roche Global Policy on Sharing of Clinical Trials Data at the following Web site:

www.roche.com/roche_global_policy_on_sharing_of_clinical_study_information.pdf

The results of this study may be published or presented at scientific congresses. For all clinical trials in subjects involving an IMP for which a marketing authorization application has been filed or approved in any country, the Sponsor aims to submit a journal manuscript reporting primary clinical trial results within 6 months after the availability of the respective CSR. In addition, for all clinical trials in subjects involving an IMP for which a marketing authorization application has been filed or approved in any country, the Sponsor aims to publish results from analyses of additional endpoints and exploratory data that are clinically meaningful and statistically sound.

The Investigator must agree to submit all manuscripts or abstracts to the Sponsor prior to submission for publication or presentation. This allows the Sponsor to protect proprietary information and to provide comments based on information from other studies that may not yet be available to the Investigator.

In accordance with standard editorial and ethical practice, the Sponsor will generally support publication of multicenter trials only in their entirety and not as individual center data. In this case, a coordinating Investigator will be designated by mutual agreement.

Authorship will be determined by mutual agreement and in line with International Committee of Medical Journal Editors authorship requirements. Any formal publication of the study in which contribution of Sponsor personnel exceeded that of conventional monitoring will be considered as a joint publication by the Investigator and the appropriate Sponsor personnel.

Any inventions and resulting patents, improvements, and/or know-how originating from the use of data from this study will become and remain the exclusive and unburdened property of the Sponsor, except where agreed otherwise.

9.6 PROTOCOL AMENDMENTS

Any protocol amendments will be prepared by PRA. Protocol amendments will be submitted to the IRB/EC and to regulatory authorities in accordance with local regulatory requirements.

Approval must be obtained from the IRB/EC and regulatory authorities (as locally required) before implementation of any changes to the study conduct, except for changes necessary to eliminate an immediate hazard to subjects or changes that involve logistical or administrative aspects only (e.g., change in Medical Monitor or contact information).

Appendix 1 Schedule of Activities (cont.)

AE = adverse event; BMI = body mass index; CG = clinical genotyping; CRU = clinical research unit; [REDACTED]; C-SSRS = Columbia-Suicide Severity Rating Scale; D = Day; ECG = electrocardiogram; FSH = follicle-stimulating hormone; IV = intravenous; PK = pharmacokinetic.

- a Subjects will be admitted to the CRU on Day -1 and will be allowed to leave when all assessments on Day 10 have been completed. Subjects will return in the afternoon of Day 14 of Period 1 (which is also Day -1 of Period 2) and will be allowed to leave when all assessments on Day 19 have been completed.
- b The IV infusion of the microdose will start 1.25 hours after the oral study drug administration on Day 1 of Period 1 and Day 14 of Period 2.
- c On Day 1 of Period 1, and Days 7 and 14 of Period 2, subjects are fasted for at least 10 hours prior to dosing. Water will be allowed ad libitum until 1 hour prior to dosing and from 1 hour after dosing. No food is allowed for at least 4 hours postdose. Standardized lunch and dinner are provided 4 and 10 hours postdose, respectively, on Day 1 of Period 1, and Days 7 and 14 of Period 2. Standardized afternoon and evening snacks will be provided as well on these days.
On the other dosing days in the multiple dosing period, subjects will be dosed at least 30 minutes prior to breakfast. On these dosing days, meals will not be standardized.
- d All PK sampling times are relative to oral dosing (see also [Appendix 2](#)).
[REDACTED]
- f Includes measurement of height and BMI.
- g Triplicate ECGs will be collected at screening and Day -1 of Period 1 only. At all other time points a single ECG will be collected (Period 1: Day 10; Period 2: Day -1 of Period 2; predose on Days 6 and 11; Day 18 (96 hours after last dosing); follow-up).
- h Vital signs will be measured at screening (in triplicate), and in Period 1: on Day -1 (in triplicate), Day 1 at 3 hours postdose, Day 2, Day 5; in Period 2: on Day -1, predose on Days 1, 7 and 14; on Day 18 (96 hours after last dosing); follow-up. At screening and on Day -1 of Period 1, vital signs will be measured in triplicate; at other time-points, vital signs will be single measurements.
- i For females only: FSH and serum pregnancy test at screening, and serum pregnancy test only at all other time points.
- j Hematology samples will be collected at screening, Day -1 of Period 1, Day -1 of Period 2; predose on Days 6 and 11 of Period 2; Day 18; follow-up.
- k Biochemistry samples will be collected at screening, Day -1 of Period 1, Day -1 of Period 2; predose on Day 11 of Period 2; Day 18; follow-up.
[REDACTED]

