1.2.1.1 Clinical Pharmacology

Plasma exposure of balovaptan increased in a greater than dose-proportional manner following single doses of 0.5 to 76 mg, whereas an approximately linear increase in exposure was observed after repeated dosing with 12 to 52 mg once daily (QD) for 14 days.

Balovaptan was rapidly absorbed with a median time to maximum observed plasma concentration (t_{max}) between 1 and 4.5 hours after administration of single doses in fasted state and between 3 and 4 hours following multiple dosing in fed state. Steady state was achieved after approximately 7 days, with an accumulation of approximately 4-fold after 12 mg QD and 2-fold after 52 mg QD; the mean apparent elimination half-life after the last dose (Day 14) was approximately 46 hours. Food had no relevant effect on the overall plasma area under the plasma concentration-time curve (AUC) of balovaptan.

In the human mass balance study (Study BP29279), an almost complete absorption of the study drug was observed within the first 72 hours following administration.

In plasma, steady state exposure to the [REDACTED] metabolite M3 was similar to or slightly higher than that of balovaptan and exposure to the [REDACTED] metabolite M2 was lower than that of parent. M3 and M2 qualify as major metabolites in plasma.

[REDACTED]

[REDACTED]

[REDACTED]

[REDACTED]

Hepatic metabolism was found to be the major pathway of elimination with the primary route of excretion via urine (approximately 53% of the material recovered, mostly

composed of metabolites). A further 30% of the administered dose was recovered in feces. The majority of excretion occurred within the first 7 days.

There was no clinically/statistically relevant PK interaction with the P-gp substrate risperidone, one of only 2 approved medications for ASD symptoms in the US, and fluoxetine, a weak CYP3A4 inhibitor often used to treat associated symptoms of ASD. Administration of a single dose of balovaptan 12 mg in combination with itraconazole, a strong CYP3A4 inhibitor, resulted in an increase in the exposure of balovaptan by 36% for maximum observed plasma concentration (C_{max}) and an approximately 3.1-fold increase for area under the concentration curve from time 0 to 120 hours (AUC_{0-120h}).

[REDACTED]

[REDACTED]

[REDACTED]

[REDACTED]

[REDACTED]

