3.3.2 Rationale for Balovaptan Dose and Schedule

A dose of 10 mg balovaptan has shown statistically significant changes in efficacy parameters in patients with ASD and is the current recommended Phase 3 dose.

In addition, a dose of 50 mg balovaptan will be studied as well to investigate any dose-dependent changes in oral bioavailability. In the MAD part of study BP25694, multiple doses of 52 mg QD in healthy subjects were well tolerated and resulted in a C_{max} of 484 ng/mL, [REDACTED]. Thus, a dose of 50 mg balovaptan QD is considered suitable to study dose-dependent changes in oral bioavailability.

Balovaptan is being developed for use in ASD, so it is expected that patients will need to take it for prolonged periods of time, likely for years or for life. Hence multiple dose testing is relevant from a clinical point of view. The multiple dose PK of balovaptan with 14 days of dosing was previously characterized in humans and was found to be time-dependent. Accumulation was observed with multiple dosing, and steady state of balovaptan was observed after approximately 7 days of dosing and after 10 days for M3. The plasma PK time course of M2 has not been closely studied but steady state has been demonstrated after 2 weeks of QD dosing with balovaptan 10 mg. Based on these observations, a dosing period of 14 days has been selected to ensure steady state plasma levels of balovaptan and its major metabolites M2 and M3 are reached and to maximize the possibility to observe any time-dependent changes in PK.

The microdose of [¹³C]-labeled balovaptan has been set to 0.1 mg; 0.1 mg is the maximum allowed IV microdose that can be administered without IV toxicity studies. Exposure after an 0.1-mg IV dose is covered by the existing nonclinical toxicity and PK

data. The t_{max} following oral dosing in the fasted state is expected to be approximately 1.5 hours postdose after a single dose and approximately 3 hours after multiple doses. To have the end of the infusion and the t_{max} of [^{13}C]-labeled balovaptan coincide with the t_{max} of the orally administered unlabeled balovaptan after a single dose, the 15-minute infusion of the microdose of [^{13}C]-labeled balovaptan will be started at 1.25 hours. For consistency the time of infusion is similar after the (last) multiple oral dose when due to accumulation plasma levels of balovaptan are predicted to not be lower than at t_{max} after the single dose.

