4.5.4 Vital Signs

Body temperature (tympanic), blood pressure, and pulse rate measurements will be collected on the days indicated in [Appendix 1](#). Blood pressure and pulse rate measurements will be performed after the subject has rested in a supine position for at least 5 minutes.

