### 17.1.4 Vital Signs

All vital signs data including derived changes from baseline will be listed. For timepoints with triplicate measurements the mean of the triplicate measurements and the change from baseline of the mean triplicate measurements will be listed by subject additionally.

Descriptive statistics will be provided to summarize vital signs including changes from baseline by treatment and scheduled time.

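### The visible schedule has no vital-sign reading near the expected peak under once-daily dosing, although vital signs are an endpoint for the safety of 10 mg and 50 mg QD

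*Protocol*

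**What the plan says.** Protocol Section 4.5.4 gives no clock times. It says that "Body temperature (tympanic), blood pressure, and pulse rate measurements will be collected on the days indicated in" Appendix 1, and footnote h there supplies the list. After triplicate readings at screening and on Day -1 of Period 1, the list reads "Day 1 at 3 hours postdose, Day 2, Day 5; in Period 2: on Day -1, predose on Days 1, 7 and 14; on Day" (Day 18, 96 hours after the last dose), and it ends with the follow-up visit. Footnote h of the SAP's Appendix 2 carries the same list.

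Protocol Section 3.3.2 expects the fasted tmax at "approximately 1.5 hours postdose after a single dose and approximately 3 hours after multiple doses". Section 1.2.1.1 reports steady state after about 7 days "with an accumulation of approximately 4-fold after 12 mg QD and 2-fold after 52 mg QD", a Day 14 half-life of about 46 hours, and a multiple-dose tmax of 3 to 4 hours in the fed state.

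Table 1 of the protocol makes vital signs an endpoint for the secondary objective on the safety and tolerability of 10 mg QD and 50 mg QD. SAP Section 17.1.4 states: "Descriptive statistics will be provided to summarize vital signs including changes from baseline by treatment and scheduled time".

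**The concern.** The plan places its one reading at 3 hours after the single dose, where the expected peak is at about 1.5 hours. It places none at 3 hours after a repeated dose, where the expected peak is at about 3 hours and exposure has accumulated two- to four-fold. No rationale for this appears in the available text.

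What is at stake is the vital-sign endpoint for the QD regimens. A short-lived change in blood pressure or pulse that tracks the peak could occur on every dosing day and leave no trace in the scheduled data for Treatments B and D. The ECGs, which also record heart rate, do not fill the gap: in Period 2 they fall on Day -1, predose on Days 6 and 11, and 96 hours after the last dose.

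**Working it through.** There is no plan figure to reproduce here. The check sets the schedule against the stated tmax and then sizes the gap.

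**Step 1: count the readings.** Period 2 vital signs under footnote h:

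| Reading | Position relative to QD dosing |
|---|---|
| Day -1 | before any QD dose |
| Day 1 predose | before any QD dose |
| Day 7 predose | trough, at about steady state |
| Day 14 predose | trough, steady state |
| Day 18 | 96 h after the last dose |
| Follow-up | 14 to 21 days after the last dose |

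Scheduled readings more than 0 and less than 24 hours after any of the 14 QD doses, other than at the next predose time: 0.

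**Step 2: size the gap.** Assumption (mine): one compartment, peak at 3 h, mono-exponential decline over the 24 − 3 = 21 h to the next predose time. The rate constant k comes from one of two stated inputs in Section 1.2.1.1:

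- half-life of 46 h: k = ln 2 / 46
- accumulation R: R = 1/(1 − exp(−24k)), so k = −ln(1 − 1/R)/24

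The half-lives of 24 h and 58 h below are not in the documents. They are back-calculated from the stated 2-fold and 4-fold accumulation.

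| Input | Half-life | R | Trough/peak = exp(−21k) | Peak/trough |
|---|---|---|---|---|
| R = 2 (52 mg QD) | 24.0 h | 2.0 | 0.545 | 1.83 |
| 46 h stated | 46 h | 3.3 | 0.729 | 1.37 |
| R = 4 (12 mg QD) | 57.8 h | 4.0 | 0.777 | 1.29 |

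The uncovered peak is about 1.3 to 1.8 times the level at the predose reading. If there is a distribution phase after the peak, the true ratio is larger.

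**Step 3: compare the covered troughs with the single-dose peak.** Under the same model, steady-state trough / single-dose peak = R × exp(−21k):

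- R = 2: 2.0 × 0.545 = 1.09
- 46 h: 3.3 × 0.729 = 2.4
- R = 4: 4.0 × 0.777 = 3.11

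So the Day 7 and Day 14 readings probably sit at or above the exposure at the single-dose peak.

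**Step 4: Day 18.** This reading is 96 − 3 = 93 h after the expected last peak. The level is then 2^(−93/half-life) of that peak: 0.07 at 24 h, 0.25 at 46 h and 0.33 at 57.8 h. It does not stand in for a reading near the peak.

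**The case against.** The strongest reply is that this is a design choice rather than an error. The protocol and SAP agree with each other. Section 3.3.1 says safety and tolerability are not a primary objective. Sections 1.3 and 3.3.2 report that the planned dosing, including 52 mg QD, was well tolerated before. Subjects are in-house during dosing, are told to report feeling unwell at once, and can have symptom-directed examinations. Nothing visible in the documents shows a peak-related effect on blood pressure or pulse. One single reading in 8 subjects per cohort without placebo would also show a modest change only poorly. All of this stands and limits the weight of the point, but none of it supplies the endpoint data.

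A reader might infer several stronger things that the documents do not support:

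- **That QD exposure goes unmonitored.** Step 3 points the other way: the troughs are probably at or above the single-dose peak.
- **That Treatments B and D have trough values only, or that the 3 h reading is the only one after a dose.** Day 18 is neither a trough nor predose, and Period 1 Days 2 and 5 also follow a dose.
- **That single and repeated dosing cannot be compared.** Period 1 Day 2 is roughly 24 h after the dose (no clock time is given), so it can be set against the QD troughs. The SAP tabulates by scheduled time, so the 3 h value need not be mixed with them. Only the 3 h comparison is missing.
- **That the Period 1 reading misses the single-dose peak.** Section 1.2.1.1 gives median single-dose tmax values from 1 to 4.5 h, so 3 h lies within that range.
- **That the lack of a reading soon after the second infusion strengthens the case.** The 0.1 mg microdose is 0.1/10 = 1% or 0.1/50 = 0.2% of the oral dose, so it adds little.

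Finally, the Appendix 1 grid is not shown, and footnote e and much of Section 5.1 are redacted. Another check there cannot be fully excluded, although footnote h reads as a complete list.

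**Conclusion.** The point holds for the visible schedule. No vital signs are scheduled near the expected 3 h peak after any QD dose, and that peak is about 1.3 to 1.8 times the predose level that is measured. The count of zero rests on footnote h being complete. The ratio rests on the one-compartment assumption, the stated 46 h half-life and the range of 24 to 58 h implied by the stated accumulation. The consequence is limited: a transient peak-related change under QD dosing would not show in the scheduled data. The primary bioavailability analysis is unaffected, and the documents give no evidence that such a change occurs. It is a gap between the safety endpoint and the protocol's own PK expectation that can be closed cheaply.

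**What to change.** Reconcile footnote h of Protocol Appendix 1, and its copy in SAP Appendix 2, with the multiple-dose tmax in Section 3.3.2. The lightest way is to take the Period 2 Day 14 vital-sign reading at the 3 h PK time that already exists in Appendix 2 of the protocol, and to keep Day 7 predose as the steady-state trough. Tabulate it under SAP Section 17.1.4 as a 3 h post-dose value, so that it lines up with the 3 h reading of Period 1. Section 4.5.9 already covers the order of vital signs and PK draws at a shared time. If the sponsor prefers predose readings, the protocol should state why. Only the timing of an assessment changes; dosing is untouched.

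Cost: subjects are already in-house, and moving the reading adds none. It leaves one steady-state trough reading instead of two and shortens the matched predose series of Days 1, 7 and 14. Keeping the Day 14 predose reading as well would cost one extra single reading per subject. Either way, a minor protocol amendment is needed under the approval rules of Section 9.6, and possibly a change to the eCRF that the SAP cites as final.
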